### SUMMARY

# **Study Title**

Mitigating the Health Effects of Desert Dust Storms Using Exposure-Reduction Approaches (LIFE+ MEDEA)

# Objectives

The primary objective of this panel study will be to quantify the vulnerability of adults with atrial fibrillation (AF) during desert dust storm (DDS) outbreaks and provide evidence-based estimates demonstrating which intervention/ recommendations work best in mitigating adverse health effects in this group of patients (primary outcome: reduction of atrial fibrillation burden by 20%) after randomization to three parallel intervention groups:

- a) no intervention for DDS
- b) intervention for outdoor exposure reduction, and
- c) interventions for both outdoor and indoor exposure reduction

The secondary objectives of the study are to:

- 1. Demonstrate which of the recommendations are effective in reducing outdoor and indoor exposures to DDS in a panel of adults with atrial fibrillation (AF)
- 2. Secondary health outcomes will be the occurrence of ventricular arrhythmias assessed through the pacemaker and heart rate variability.

# **Design, Interventions and Outcomes**

Type of study: Public Health Intervention Study

Intervention: Patients with AF will be recruited and will be randomized during the high DDS outbreaks season (Spring 2019 and 2020) with 1:1:1 ratio into three parallel groups to receive:

- a) No intervention for DDS.
- b) Intervention for outdoor exposure reduction, by reducing the time spend outdoors and by avoiding physical activity.
- c) Interventions for outdoor (as above) and indoor exposure reduction (by minimizing home ventilation and filtering indoor air).

Disease-related adverse health outcomes will be assessed in the three parallel arms of the study.

Approaches for delivering the intervention:

• A bidirectional, patient-centered e-Platform will be developed in order to facilitate prompt communication with the participants and provide early warnings regarding forecasted

upcoming DDS events through text messaging and smartphone applications. Furthermore, the same IT platform and mobile application will be utilised for the dissemination of the exposure reduction guidelines that the participants will follow, depending on which arm of the study they have been randomised to.

Assessment of adherence to intervention:

- Monitor compliance to exposure-reduction guidelines using remote sensors. The intervention for outdoor exposure reduction, entailing reduction of the time spend outdoors and avoidance of physical activity, will be assessed with the use of smart wristwatches that will have a global position system (GPS) and an accelerometer.
- The intervention for indoor exposure reduction, entailing minimization of home ventilation and filtering of indoor air, will be assessed with the use of particle samplers that will be placed outside and inside of houses and school classrooms.

## Assessment of health outcomes:

- Daily recordings of AF/ventricular arrhythmia episodes from the participants' pacemakers during the 4-month study period will be downloaded with interrogation of the pacemaker during a visit to the Arrhythmia Clinic after the end of the monitoring period.
- Phone interviews every 1 month throughout the high DDS period recording symptoms of fatigue, change in medication use, and unscheduled visits to health professionals for heart arrhythmias/episodes.
- Continuous recordings of biological parameters (pulse rate, pulse rate variability, temperature) will be obtained by wearing smart watch sensors that will be uploaded on line to e-platform.

Primary health outcome will be every detected high atrial frequency episode of >330 ms (180 beats per minute) lasting for longer than 30 s with an atrial sensitivity of 0.5 mV (assumed as an episode of AF). AF burden is defined as the overall time percentage with AF during the observed period. For the primary analysis, we will compare the combined effect in the two intervention groups versus the control group. Secondarily, the effectiveness of each intervention will be compared versus the control group and to each other.

Secondary health outcomes will be the occurrence of ventricular arrhythmias assessed through the pacemaker and heart rate variability.

# Duration

Duration of the study: A feasibility (pilot) trial and refinement of protocols and tools will be performed during the high DDS outbreaks season of 2018. During the fall of 2018 and 2019, MEDEA personnel will initiate the recruitment procedure to enrol eligible AF patients for the two

main study periods (high DDS outbreaks season of February to May 2019 and 2020). Data collection, data cleaning and statistical analysis will take place in 2020.

# **Study Population**

Study population, sample size and location: Men and women with prior implantation of a dual lead (atrial and ventricular) pacemaker or ICD, will be recruited from cardiac arrhythmia clinics in General Hospital in Nicosia-Cyprus (n=156) in project years 2018-2019 and 2019-2020. Recruitment of participants will be facilitated through the network of physicians in Nicosia General Hospital. In order to facilitate recruitment, relations will be established with the Administrative and Nursing staff of the Clinics and Patients' Associations and the details of the project will be explained to them. During fall 2018 and 2019, MEDEA personnel will start recruitment efforts to detect eligible AF patients for participation in the study in the high DDS periods of February-May 2019 and 2020.

The same number of patients will be recruited in each study site (Beer Sheba, Heraklion, Nicosia) and we expect that a total of 468 AF patients will be recruited. We estimate a dropout rate of 30%, which will eventually give us 324 AF patients to analyse. The feasibility of protocols to assess health outcomes in vulnerable patient groups will be tested in the pilot study during the high DDS outbreaks season of 2018 with and without implementation of exposure reduction guidelines in all study sites in a small number of patients (6 AF patients per study site).

# 1 WORKING HYPOTHESIS

We hypothesize that there will be a reduction of the total AF burden compared to the control group in:

- a) The group with intervention aimed to outdoor exposure reduction (b).
- b) The group with intervention aimed to outdoor and indoor exposure reduction (c).
- c) Both (b) and (c) groups combined as compared to the control.

# 2 STUDY OBJECTIVES

# 2.1 Primary Objective

The primary objective of this panel study will be to quantify the vulnerability of adults with atrial fibrillation (AF) during DDS outbreaks and provide evidence-based estimates demonstrating which intervention/ recommendations work best in mitigating adverse health effects in this group of patients (primary outcome: reduction of atrial fibrillation burden by 20%) after randomization to three parallel intervention groups:

- a) no intervention for DDS
- b) intervention for outdoor exposure reduction, and
- c) interventions for both outdoor and indoor exposure reduction

The primary health outcome will be defined by using every detected high atrial frequency episode of >330 ms (180 beats per minute) lasting for longer than 30 s with an atrial sensitivity of 0.5 mV (assumed as an episode of AF). AF burden is defined as the overall time percentage with AF during the observed period. For the primary analysis, we will compare the combined effect in the two intervention groups versus the control group. Secondarily, the effectiveness of each intervention will be compared versus the control group and to each other.

# 2.2 Secondary Objectives

The secondary objectives of the study are to:

- 1. Demonstrate which of the recommendations are effective in reducing outdoor and indoor exposures to DDS in a panel of adults with atrial fibrillation (AF)
- 2. Secondary health outcomes will be the occurrence of ventricular arrhythmias assessed through the pacemaker and heart rate variability.

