# 4 STUDY DESIGN

Type of study: Randomized clinical trial (Behavioural Intervention)

Patients with AF will be recruited during DDS outbreaks and will be randomized into three parallel groups to receive:

- a) No intervention for DDS,
- b) Intervention for outdoor exposure reduction, and
- c) Interventions for both outdoor and indoor exposure reduction.

Disease-related adverse health outcomes will be assessed in all the parallel arms of the study.

Previous publications of the MEDEA partners (Achilleos et al, 2014; Gerasopoulos et al, 2006; Krasnov et al, 2014), indicated that 2/3 of each year's DDS events in the Eastern Mediterranean region appear during February-May, with 10-15% of the days during this period being "DDS days". Thus we will perform this public health intervention study during February–May of 2019 and 2020.

Study population and location: Men and women with prior implantation of a dual lead (atrial and ventricular) pacemaker or ICD, will be recruited from the cardiac arrhythmia clinic at the Nicosia General Hospital of Cyprus (n=156) in project years 2018-2019 and 2019-2020. Each patient will have assessment of health outcomes during only one high DDS period.

Duration of the study: A feasibility trial and refinement of protocols and tools will be performed in the high DDS period of 2018. In the fall of 2018 and 2019, MEDEA personnel will start recruitment efforts to detect eligible AF patients for participation in the study during the high DDS periods of February-May 2019 and 2020.

Assessment of health outcomes:

- The occurrence of AF/ventricular arrhythmia episodes will be recorded daily using the already implanted participants' pacemakers or ICD during the 4-month study period. The recorded episodes will be downloaded with interrogation of the pacemaker or ICD during a visit to the Arrhythmia Clinic after the end of the study period.
- Phone interviews every 1 month throughout the high DDS outbreaks season will be carried out. Data collected will include symptoms of fatigue, change in medication use and unscheduled visits to health professionals for heart arrhythmias/episodes.
- Continuous recordings of biological parameters (pulse rate, pulse rate variability and temperature) obtained by wearing smart watch sensors and uploaded on line to the secure e-platform.

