# 5 SELECTION AND ENROLLMENT OF PARTICIPANTS

# 5.1 Inclusion Criteria

The inclusion criteria for this panel study will be patients with permanent dual lead (atrial and ventricular) pacemaker or ICD implanted at least two months prior to randomization, with:

- A history of AF or
- Detection of AF in pacemaker/ICD monitoring (continuous recording)

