# 11 DATA COLLECTION

## **11.1 Data Collection Forms**

Health assessment data:

- The baseline demographic (gender, age, city), medical, medication and symptom data will be obtained using surveys/questionnaires.
- Daily recordings of AF/ventricular arrhythmia episodes will be obtained from the participants' pacemakers.
- Symptoms of fatigue, change in medication use, and unscheduled visits to health professionals for heart arrhythmias/episodes will be recorded via phone interviews.
- Continuous recordings of biological parameters (pulse rate, pulse rate variability, temperature) obtained by wearing smart watch sensors.

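### Ventricular arrhythmia is recorded from both pacemakers and ICDs, but no between-arm analysis uses device type; adding it is a free and probably modest gain in precision for a secondary outcome

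*Protocol*

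**What the plan says.** **Enrolment.** Protocol Section 5.1 admits "patients with permanent dual lead (atrial and ventricular) pacemaker or ICD implanted at least two months prior to randomization". The Summary (Study Population) and Section 5.3 also name both devices.

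**Source of the data.** Section 4 covers both: "The occurrence of AF/ventricular arrhythmia episodes will be recorded daily using the already implanted participants' pacemakers or ICD during the 4-month study period". On retrieval it adds: "The recorded episodes will be downloaded with interrogation of the pacemaker or ICD during a visit to the Arrhythmia Clinic".

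**Shorter wording elsewhere.** Section 2.2 mentions only the pacemaker: "Secondary health outcomes will be the occurrence of ventricular arrhythmias assessed through the pacemaker and heart rate variability". The Summary (Objectives, and Assessment of health outcomes) does the same, as does Section 11.1: "Daily recordings of AF/ventricular arrhythmia episodes will be obtained from the participants' pacemakers". The SAP's section on health outcomes in AF patients refers to pacemaker recordings and never mentions ICDs.

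**Analysis.** Section 7.2.2 randomises 1:1:1 and names no stratification factor. Protocol Section 8.2.2 and the SAP list t-tests, repeated-measures ANOVA, their non-parametric counterparts and chi-square. The hierarchical Poisson model is for AF episodes. The SAP sends secondary outcomes to its Equations 1 to 4, whose covariate list covers time-activity, housing, weather, vegetation, land use and emissions. Device type appears in none of these.

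**The concern.** Two kinds of device carrier are pooled for an outcome whose frequency could differ between them. If it does, device type is a baseline predictor available at no cost, and leaving it out of the arm comparison keeps avoidable variation in the error term. At stake is the precision of one secondary outcome for which the plan states no power. The validity of the comparison is not at stake.

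**Working it through.** **1. Are ICD data collected?** Yes. Section 4 is the fullest account of how episodes are recorded and downloaded, and it names the ICD at both steps. The pacemaker-only sentences give no instruction to exclude ICD records.

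**2. Does any planned analysis already recover the precision?** No.
- The case-crossover compares each patient with their own control periods, so device type cancels. As specified, however, it estimates the association of dust storms with arrhythmia, not the difference between arms.
- The subject-specific intercepts in Equation 1 absorb device type for within-patient slopes. Arm varies between patients, so for the arm contrast a device effect stays in the between-patient variance.
- The Poisson model has a different outcome (AF episodes).

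**3. The plan's own figure.** None exists for ventricular arrhythmia. The only AF-study power is 81% for AF burden. Recomputed from the SAP's inputs (Weibull mean/SD 15/15 v 12/15, 108 v 216, two-sided Wilcoxon at 0.05), it comes to about 76%. That is a separate matter and does not enter below.

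**4. Inputs.** From the documents: 108 control v 216 combined intervention, two-sided alpha 0.05. Assumed, because the documents are silent: ICD share 10–50%; control risk of at least one episode 10–20% with a pacemaker and 10–60% with an ICD; odds ratio 0.5 within each device type.

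**5. One case by hand.** ICD share 30%, control risks 10% (pacemaker) and 30% (ICD).
- Intervention odds: 0.5 × 0.10/0.90 = 0.0556, risk 0.0526; 0.5 × 0.30/0.70 = 0.2143, risk 0.1765.
- *Ignoring device type.* Control 0.7 × 0.10 + 0.3 × 0.30 = 0.160. Intervention 0.7 × 0.0526 + 0.3 × 0.1765 = 0.0898. Difference 0.0702. Pooled risk (108 × 0.160 + 216 × 0.0898)/324 = 0.1132. Null SE = √[0.1132 × 0.8868 × (1/108 + 1/216)] = 0.0373. Alternative SE = √[0.160 × 0.840/108 + 0.0898 × 0.9102/216] = 0.0403. z = (0.0702 − 1.96 × 0.0373)/0.0403 ≈ −0.07, so power is about 47%.
- *Stratified (Mantel-Haenszel).* Weights n₀n₁/(n₀+n₁): pacemaker 75.6 × 151.2/226.8 = 50.4; ICD 32.4 × 64.8/97.2 = 21.6. Numerator 50.4 × 0.0474 + 21.6 × 0.1235 = 5.06. Pooled risks within strata: (0.10 + 2 × 0.0526)/3 = 0.0684 and (0.30 + 2 × 0.1765)/3 = 0.2176. Null SD = √[50.4 × 0.0684 × 0.9316 + 21.6 × 0.2176 × 0.7824] = 2.62. Alternative SD = √[50.4² × (0.10 × 0.90/75.6 + 0.0526 × 0.9474/151.2) + 21.6² × (0.30 × 0.70/32.4 + 0.1765 × 0.8235/64.8)] = 2.82. z = (5.06 − 1.96 × 2.62)/2.82 ≈ −0.03, so power is about 49%.

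Simulation (10,000 replicates) gives 46.5% and 48.0% for the same case. The gain is 1.5 to 2 points.

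**6. Range, yes/no outcome** (simulation, ICD share 10–50%):

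| Control risk, pacemaker v ICD | Gain from stratifying (power points) |
|---|---|
| 10% v 10% | about 0 |
| 10% v 20% | 0–1 |
| 10% v 30% | 1–2 |
| 10% v 50% | 4–7 |
| 20% v 60% | 3–7 |

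The largest gain is at ICD share 50% and 10% v 50%: power rises from 57.6% to 64.5%. Without device type, type I error is 4.5–5.1%.

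**7. Range, counts** (negative binomial, pacemaker mean 1 event, dispersion 1.5, rate ratio 0.6 between arms; 600 replicates, simulation error about 2 points). The gain from adding device type is about 0 points at equal rates, 1–4 at a two-fold difference between devices, 2–5 at three-fold and 9–12 at five-fold.

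**The case against.** **A stronger reading is tempting.** A reader of Section 2.2 alone might infer that ICD records are left out, and with them many of the events. In the case worked above, ICD carriers would hold 0.3 × 0.30/(0.3 × 0.30 + 0.7 × 0.10) = 0.09/0.16 = 56% of control-level events, and a pacemaker-only test would have about 28% power instead of 46%. The documents do not support that reading. Section 4 names the ICD for both recording and download. Section 11.1 uses one phrase for AF and ventricular episodes together, so taken literally it would also remove enrolled ICD carriers from the primary outcome. The short wording is loose usage, and no loss of patients or events should be claimed.

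**Chance imbalance.** A reader might also infer that an uneven ICD share between arms distorts the result. Randomisation makes this ordinary sampling variation, which the test already allows for. The type I error figures agree.

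**The premise is not in the documents.** They say nothing about why ICDs were implanted or how often either group has ventricular arrhythmia. This objection stands: higher risk in ICD carriers is an assumption, and the benefit disappears if risk is equal. The yes/no and count forms are assumed too, since the plan fixes neither.

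**It is only a secondary outcome with no stated power.** This also stands, and it keeps the point minor.

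**The within-patient analyses make it irrelevant.** This does not stand for the arm comparison, for the reasons in step 2 of the working.

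**Conclusion.** A minor point that costs nothing to act on. Device type is absent from every between-arm analysis of ventricular arrhythmia although it is known for all patients before randomisation. The precision given up is conditional: about 0–7 power points for a yes/no outcome at odds ratio 0.5, up to about 12 for counts if rates differ five-fold, and nothing if the devices carry the same risk. ICD share, event rates and effect sizes are all assumed. Omitting device type is not an error that biases the comparison or inflates type I error. The pacemaker-only wording is an editorial inconsistency, because Section 4 already settles the data source.

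**What to change.** 1. In the SAP, state the form of the ventricular arrhythmia outcome (occurrence or count) and prespecify device type, pacemaker v ICD, in its between-arm analysis. Use a Mantel-Haenszel stratum for occurrence, or a covariate in a logistic or count model.
2. Show the results by device, descriptively with confidence intervals. The strata may be small: a 30% ICD share of 324 is about 97 patients.
3. As an editorial matter, bring the Summary (Objectives; Assessment of health outcomes), Section 2.2, Section 11.1 and the SAP's section on AF patients into line with the pacemaker-or-ICD wording of Section 4.

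The cost is a few words and one covariate already known from the inclusion criterion. It needs no extra patients or measurements and no change to the randomisation. If device type proves uninformative, the simulated cost in power is within about 0.2 points for the yes/no analysis and within simulation error for counts.

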# 3 BACKGROUND AND RATIONALE

# 3.1 Background on Condition, Disease, or Other Primary Study Focus

The MEDEA project is envisioned to provide the field-based evidence for the adoption of a strategic plan for mitigating the health effects of desert dust storm (DDS) events in South-Eastern Europe. Over the past decade, several studies have demonstrated that DDS in Mediterranean countries, originating mostly from the Sahara and Arabian Peninsula deserts, have been increasing in number and magnitude and linked it to desertification, climatic variability and global warming. EU legislation considers DDS impossible to prevent, implicitly harmless and discounts their contribution to daily and annual air quality standards of particulate matter up to 10 microns (PM10).

However, there is increasing evidence from epidemiological studies which correlates exposure to PM10 during DDS with a significant increase in mortality and hospital admissions from cardiovascular and respiratory causes. Therefore, there is a pressing need for EU policies to reduce population exposures and increase individual, population and institutional resilience to the growing frequency and intensity of DDS.

MEDEA ultimate goal is to demonstrate the feasibility and effectiveness of an adaptation strategy to DDS and better inform EU policy making.

# 3.2 Study Rationale

#### Desert dust storm events across Southern Europe

A dust storm is a phenomenon common to arid and semi-arid regions. In the EU, the term "Desert Dust Storms (DDS)" is used in the context of sandstorms originating primarily from the Sahara desert but also from the Arabian–Negev desert. The term DDS refers to the condition created when finer sand particulate matter (PM) from the desert surface is transported over a long distance. DDS pose a major risk to populations residing in affected areas, such as in Mediterranean countries belonging to the global dust belt, extending from West Africa to the Arabian Peninsula (Querol et al., 2009). During DDS events, which can last for several days,  $PM_{10}$  levels are considerably higher than the 2005 EU daily limit value of 50 µg/m^3 (Achilleos et al, 2014). Dust PM is mostly composed of rock-forming and clay minerals and they may carry microbial agents, such as bacteria, fungi and viruses (Griffin et al, 2007), and mix with anthropogenic atmospheric pollutants during transport.

#### Associations of DDS with mortality and hospital admissions

Historically, DDS were not considered harmful to humans due to their natural origin and crustal composition; however, in recent years, a large number of studies worldwide and in particular from Cyprus (Middleton et al., 2008; Neophytou et al., 2013), Greece (Samoli et al., 2011), Italy (Mallone et al., 2011) and Israel (Vodonos et al., 2014) have reported associations of PM10 during DDS outbreaks with increased hospital admissions for asthma, chronic obstructive pulmonary disease, cardiovascular disease and increased mortality. The pathogenic effect of PM10 inhalation has been attributed to direct physical and toxic action of particles on human airway epithelium and systemic inflammatory responses triggering endothelial dysfunction or dysfunction of the autonomic nervous system (Leski et al., 2011). Increased hospital admissions and mortality are only two of a much larger number of adverse outcomes of exposure to DDS  $PM_{10}$ . Beyond these serious complications, patients suffer symptomatic exacerbations of pre-existing conditions, require unscheduled hospital visits, use excessive medications, and lose their sense of well-being, often with days off work or school. These relatively less studied consequences are more common, but largely un-quantified and un-investigated. Finally, DDS  $PM_{10}$  exposure is associated with sub clinical effects on the general population, from mild discomfort, eye and skin irritation to substantial effects on biological processes and quality of life.

